6.1.2.3. Dosage and Administration

Temozolomide will be administered PO QD, preferably in the morning (see dosing schedule below [Table 2](#)). TMZ can be administered with pamiparib. The daily dose and schedule will be determined as outlined in Section [4.2.1](#).

Patients will be instructed to swallow the capsules whole, in rapid succession, with water. Patients will be required to fast for at least 2 hours before and one hour after each TMZ administration. Water is allowed during the fasting period.

A dose of TMZ should be skipped if it is not taken within 2 hours of the scheduled time. An extra dose of TMZ should not be taken to make up for a missed dose. If vomiting occurs during the course of treatment, no re-dosing of the patient is allowed before the next scheduled dose.

In this study, TMZ will be administered as a flat dose rather than based on body surface area (BSA). The conversion of dose levels for TMZ for this study into BSA-based doses are as follows in [Table 2](#).

Table 2: Comparison of Temozolomide Dosing: Flat fixed versus BSA-based

Flat Dose QD	BSA Equivalent ¹
20 mg	11.5 mg/m ²
40 mg	23.0 mg/m ²
60 mg	34.7 mg/m ²
80 mg	46.0 mg/m ²
120 mg	69.0 mg/m ²

BSA = body surface area; QD = once daily

¹ Dose equivalent information is provided for reference only and assumes an average body surface area of 1.73 m²

On days with PK assessments, pamiparib and TMZ should be administered in the clinic.

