7.8.2. PK of TMZ

Pharmacokinetic samples will be collected from patients in all cohorts at the following timepoints: pre-dose (within 30 min prior to dose) and 1 hour (± 15 min) post dose on Cycle 1 Day 1 and Cycle 1 Day 7. The time of study drug administration on the day prior to Cycle 1 Day 7 must be recorded on the eCRF.

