8.3.2. Cycle 1 (28 days)

During Cycle 1, all assessments (except for PK post-dose blood collection) performed during the clinic visit must be done **prior** to study drug administration. On days with PK assessments, pamiparib (first dose) and TMZ should be administered in the clinic.

For the Dose Expansion Cohorts, a 2-day window is allowed during Cycle 1 visits.

A list of all of the activities during Cycle 1 is found in the Schedule of Assessments Table ([Appendix 1 Table 1](#)).

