14. APPENDICES

APPENDIX 1. SCHEDULE OF ASSESSMENTS

Appendix 1 Table 1: Schedule of Assessments and Procedures Schedule for Dose Escalation and Dose Expansion Phases

Assessments	Pre-Screening (Dose Expansion only) ¹	Screening ²	Cycle 1 (28 days)				Cycles 2- 5 (28 days)		Cycle 6 and Subsequent Cycles in 1st year (Every 28 days)	Subsequent Cycles in the 2nd year and beyond (Every 28 days)	EOT ³	Safety Follow-up ⁴	Efficacy Follow-Up	Survival Follow-Up ⁵
			1	7	15	22	1	15						
Day of Phase	-84 to -29	-28 to -1	1	7	15	22	1	15	1	1	~7 days after last dose	~30 ± 7 days after last dose	Every 8 weeks	Every ~3 months
Allowed time window				-2 days ⁶	± 2 days	± 2 days	± 2 days ⁶	± 2 days	± 3 days	± 3 days			±7 days	
Pre-screening informed consent	X													
Informed consent		X												
Baseline demographics		X												
Medical and cancer history		X												
Complete Physical examination ⁷		X									X			
Limited physical examination ⁸			X	X	X	X	X	X	X	X				
Vital signs (including weight)		X	X	X	X	X	X	X	X	X	X			
Height		X												
ECOG performance status		X	X				X		X	X	X			
12-lead ECG ⁹		-14 to -1 X									X			
Triplicate ECGs ¹⁰			X		X									
Hematology ¹¹		-14 to -1 days X ¹²	X	X	X	X	X	X	X	X	X			
Clinical chemistry ¹¹		-14 to -1 X ¹²	X	X	X	X	X	X	X	X	X			

Assessments	Pre-Screening (Dose Expansion only) ¹	Screening ²	Cycle 1 (28 days)				Cycles 2- 5 (28 days)		Cycle 6 and Subsequent Cycles in 1st year (Every 28 days)	Subsequent Cycles in the 2nd year and beyond (Every 28 days)	EOT ³	Safety Follow-up ⁴	Efficacy Follow-Up	Survival Follow-Up ⁵
			1	7	15	22	1	15	1	1				
Day of Phase	-84 to -29	-28 to -1	1	7	15	22	1	15	1	1	~7 days after last dose	~30 ± 7 days after last dose	Every 8 weeks	Every ~3 months
Allowed time window				-2 days ⁶	± 2 days	± 2 days	± 2 days ⁶	± 2 days	± 3 days	± 3 days			±7 days	
Coagulation		-14 to -1 X ¹²												
Urinalysis ^{11,13}		-14 to -1 X ¹²												
Serum pregnancy test ¹⁴		-7 to -1 X												
Urine pregnancy test ¹⁵							X		X	X	X			
CT or MRI ¹⁶		X	EVERY 8 WEEKS ± 7 DAYS								X		X	
Tumor antigens ¹⁷		X	EVERY 8 WEEKS ± 7 DAYS								X		X	
HBV/HCV tests ¹⁸		X	As clinically indicated											
TMZ Dosing Dose escalation			Pulsed Dosing (Arm A): Once daily on Days 1 to 7 or Days 1-14 of each 28 day cycle Continuous Dosing (Arm B): Once daily continuously											
TMZ Dosing Dose Expansion			RP2D= 60 mg QD 60 mg QD Days 1-7 of each cycle											

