- The EOT visit will occur within 7 days after a patient permanently discontinued study drugs for any of the reasons outlined in Section 8.4. A visit should be scheduled as soon as possible, but the EOT visit may occur later after discussion with the Medical Monitor for specific circumstances, such as prolonged hospitalization. The visit at which CT or MRI showed progressive disease may be used as the EOT visit provided that all required assessments were performed. If routine laboratory tests (e.g., hematology, clinical chemistry) were completed ≤ 7 days before the EOT Visit, these tests do not need to be repeated. The CT/MRI does not have to be repeated if it was performed within 14 days of the EOT visit or at a prior response evaluation that documented progressive disease. ECG does not have to be repeated if it was performed within 14 days of the EOT visit. If the EOT Visit did not occur until 30 days (± 7 days) or later after the last dose of pamiparib and TMZ, the EOT Visit may also be used as the Safety Follow-up Visit.
- All patients who permanently discontinue study drugs will have a safety follow-up approximately 30 days after the last day of study drugs to collect AEs and SAEs that may have occurred after the patient discontinued from the study drugs. If the patient does not require any laboratory assessments, the investigator or his/her designee will contact the patient to collect this information. (Protocol Section 8.5.1).
- Following permanent discontinuation of study drugs and/or Safety Follow-up parts of the study, every effort should be made to follow up with all patients by phone every 3 months for their survival status until patient death (Protocol Section 8.5.3).

6. A window of ± 2 days on Cycle 1 Day 7 and Cycle 2 Day 1 is allowed during **Dose Expansion Only**.
7. Complete physical examination includes the following items: 1) general appearance; 2) head, eyes, ears, nose, and throat; 3) neck; 4) heart; 5) chest (including lungs); 6) abdomen; 7) extremities; 8) skin; 9) lymph nodes; 10) cardio-vascular; 11) neurological status.
8. A limited physical examination should be directed at the evaluation of symptoms or specific safety issues. Changes from baseline abnormalities should be recorded at each subsequent physical examination. New or worsening abnormalities should be recorded as AEs if appropriate.
9. A single 12-lead ECG will be performed during Screening within 14 days of Cycle 1 Day 1 and at the EOT visit.

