17. Blood tumor antigens such as CA-125 for ovarian cancer and PSA for castration-resistant prostate cancer will be tested during screening and every 8 weeks ± 7 days after the first dose of pamiparib in local laboratories. The CA-125 responses must be confirmed and maintained for at least 28 days. Patients can be evaluated according to CA-125 only if they have a pretreatment sample that is at least twice the upper limit of the reference range and within 2 weeks before starting the treatment.
18. Testing will be performed by local laboratory at screening and as clinically indicated and will include HBV/HCV serology (hepatitis B surface antigen, hepatitis B surface antibody, hepatitis B core antibody, and HCV antibody) and viral load assessment (HBV DNA and HCV RNA).
19. Concurrent medications will be collected during screening and on the first day of study. Changes to Concurrent medications will be collected during subsequent clinic visits.
20. Pharmacokinetic (PK) samples will be collected at the following timepoints: For pamiparib: ≤ 30 min before pamiparib and TMZ dosing, 1 (± 15 min), 2 hours (± 30 min), and 4 hours (± 30 min) after pamiparib dose on Cycle 1 Day 1 and Cycle 1 Day 15; For TMZ: on Cycle 1 Day 1 and Day 7 at ≤ 30 min before dosing and 1 hour (± 15 min) after TMZ dose.
21. Blood samples must be collected at screening or on Day 1 for the assessment of germline *BRCA* and/or other mutation analysis (8 ml). In addition, two blood samples (10 mL each) must be collected for plasma markers (e.g., CNA), TMZ treatment, and PARP inhibition **before** study treatment on Day 1 and

Day 15, and at the EOT visit (unless one had been collected within 14 days). Instructions for the processing, storage, and shipping of samples will be provided in the Study Manual.

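### In expansion, the ±2-day window lets the Cycle 1 Day 7 visit fall after pulsed temozolomide has stopped: the 1-hour PK sample is impossible on Days 8 and 9, and the 24-hour trough is lost on Day 9

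*Protocol*

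**What the plan says.** **Dosing.** The expansion row of Protocol Appendix 1 Table 1 gives TMZ as "60 mg QD Days 1-7 of each cycle".

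**Sampling.** Protocol Section 7.8.2 opens with "Pharmacokinetic samples will be collected from patients in all cohorts at the following timepoints". It then asks for a sample within 30 minutes before the dose and another at 1 hour (±15 min) "post dose on Cycle 1 Day 1 and Cycle 1 Day 7". Footnote 20 of the table agrees: "For TMZ: on Cycle 1 Day 1 and Day 7 at ≤ 30 min before dosing", then 1 hour after the TMZ dose. Section 7.8.2 adds: "The time of study drug administration on the day prior to Cycle 1 Day 7 must be recorded on the eCRF". Section 6.1.2.3 says: "On days with PK assessments, pamiparib and TMZ should be administered in the clinic".

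**Visit window.** Three places speak to it, and they differ:
- The table header gives minus 2 days for Cycle 1 Day 7, with a marker to footnote 6. Days 15 and 22 of the same cycle have ±2 days.
- Footnote 6: "A window of ± 2 days on Cycle 1 Day 7 and Cycle 2 Day 1 is allowed during" dose expansion only.
- Section 8.3.2: "For the Dose Expansion Cohorts, a 2-day window is allowed during Cycle 1 visits", with no direction given.

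**Analysis.** PK parameters of both drugs, with trough concentration named, are a secondary endpoint (Protocol Section 3.2, SAP Section 4.2). SAP Section 6.3.6 summarizes TMZ trough and/or peak and compares them with a historical control. The PK Analysis Set in SAP Section 6.1 admits any treated patient with at least one plasma concentration.

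**The concern.** A site that sees an expansion patient on Day 8 or 9 has complied with footnote 6, but TMZ ended on Day 7 and the sampling instruction refers to a dose that is not given that day. Because the visit is inside its window, nothing flags a deviation and nothing prompts a correction.

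The timepoint cannot be replaced from elsewhere. The Day 1 pre-dose sample precedes any TMZ, so Day 7 is the only source of a TMZ trough and the only peak after repeated dosing. Protocol Section 4.3 says PK assessments in expansion will be the same as in escalation, yet footnote 6 relaxes the timing in expansion alone.

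At stake are the completeness and correct timing of the repeat-dose TMZ concentrations in the expansion cohorts. DLT, adverse-event and response endpoints are not affected.

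**Working it through.** The plan states no figure to reproduce. The check is a count of calendar days.

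**Inputs**
- TMZ dosing days in expansion: 1 to 7 (Appendix 1 Table 1).
- Permitted visit days under footnote 6: 7 − 2 = 5 through 7 + 2 = 9.
- Permitted visit days under the header: 7 − 2 = 5 through 7.
- TMZ is taken once daily at about the same clock time. This is an assumption; Section 6.1.2.3 says once daily, preferably in the morning.

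**Formula.** Hours since the last dose at the usual dosing time = 24 × (visit day − last dosing day before the visit).

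| Visit day | In header window | In footnote 6 window | TMZ dose that day | Hours since last dose | 24-hour trough | 1-hour post-dose sample |
|---|---|---|---|---|---|---|
| 5 | yes | yes | yes | 24 × (5 − 4) = 24 | yes | yes |
| 6 | yes | yes | yes | 24 × (6 − 5) = 24 | yes | yes |
| 7 | yes | yes | yes | 24 × (7 − 6) = 24 | yes | yes |
| 8 | no | yes | no | 24 × (8 − 7) = 24 | yes, if drawn at the usual time | no |
| 9 | no | yes | no | 24 × (9 − 7) = 48 | no | no |

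**Result by window**
- Footnote 6: the post-dose sample is impossible on 2 of 5 permitted days, and the 24-hour trough is lost on 1 of 5.
- Header: 0 of 3 permitted days fall outside TMZ dosing.

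**Patients affected.** The documents do not say how visits will spread over the window, so this part rests on an assumed 10-20% of visits falling on Day 8 or 9.
- Six cohorts of 20-25 give 6 × 20 = 120 to 6 × 25 = 150 patients. Affected: 0.10 × 120 = 12 to 0.20 × 150 = 30.
- With the stated expansion total of about 200, affected: 0.10 × 200 = 20 to 0.20 × 200 = 40.

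These counts are patients without a post-dose sample. The number who also lose the trough lies between none and all of them, depending on the split between Days 8 and 9.

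**The case against.** **The window conflict may be only editorial.** The header cell carries the marker to footnote 6, so the footnote can be read as a deliberate exception for expansion, and the undirected window in Section 8.3.2 is compatible with minus 2 days. That stands as far as it goes: only footnote 6 prints ±2 days. But even as a deliberate exception, it collides with Days 1-7 dosing and dose-linked sampling, and no passage ties the TMZ draw to a dosing day.

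**Day 8 is not a lost trough.** This is correct. A morning draw on Day 8 is about 24 hours after the Day 7 dose, the same interval as any other pre-dose sample. A reader might infer that every late visit loses both samples, or that 40% of expansion Day 7 samples would be invalid. The documents do not support either. The 2-in-5 share is a share of permitted days and applies only to the post-dose sample. It becomes a share of samples only if visits are spread evenly over Days 5 to 9, for which the documents give no basis.

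**Downward bias is not shown.** A reader might also infer that low off-dose values will pull down the trough and peak summaries and the comparison with historical control. Because the instructions tie each sample to a dose, a site following them on Day 8 or 9 has no post-dose clock and may simply record nothing. Missing values are at least as likely as low ones, so no direction of bias is established. Nor does anything authorize a TMZ dose after Day 7 to meet the PK instruction.

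**The SAP may not be the place for the rule.** SAP Section 1 says PK detail may sit in a separate plan, and SAP Section 6.4.1 lists all dosing records, so an undosed day can be identified. Both points are fair. The lack of a rule in Section 6.3.6 shows only that the available documents contain none.

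**The effect is limited.** Footnote 6 excludes escalation, so those patients (about 50) keep minus 2 days. Day 1 sampling is unaffected, and the TMZ analysis is descriptive with no hypothesis test.

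**Conclusion.** The inconsistency is real. In expansion, a visit inside the footnote 6 window can fall on a day when the required TMZ post-dose sample cannot be taken (Days 8 and 9), or when a pre-dose draw is no longer a 24-hour trough (Day 9). These day counts follow from the protocol's own text, given once-daily dosing at a stable clock time.

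The consequence is missing or mistimed values at the only repeat-dose TMZ timepoint, for a named but descriptive secondary endpoint. How many patients are affected is not known from the documents; the counts above hold only under the assumed 10-20% of late visits. The point is moderate in weight and worth correcting because the correction is small.

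**What to change.** 1. **Protocol, footnote 6 and Section 8.3.2.** Bring both into line with the table header by stating minus 2 days for the Cycle 1 Day 7 visit in expansion. Alternatively, keep the wider visit window but require the TMZ PK draw on a day when TMZ is given under the existing schedule. Keep ±2 days for Cycle 2 Day 1.
2. **SAP Section 6.3.6, or the separate PK plan.** Exclude from the peak summary any Day 7 sample with no TMZ dose recorded that day. Exclude from the trough summary any sample not about 24 hours after the previous dose. A Day 8 morning draw would then count towards the trough but not the peak.

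Neither step implies any change to TMZ dosing. The cost is a short edit in two protocol places and a sentence or two in the analysis plan, with slightly less scheduling flexibility at one visit.

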Patients who permanently discontinue study drugs prior to progressive disease will continue with regular tumor assessments as per protocol every 8 weeks (± 7 days) until disease progression, administrative issues, start of other anticancer therapy or any other reason listed in [Section 8.4](#), whichever occurs first. This imaging schedule will be maintained regardless of any intermediate unscheduled scans. Patients who withdraw from the study for clinical or symptomatic deterioration before objective documentation of progressive disease will be requested to undergo appropriate imaging to confirm progressive disease. Every effort will be made to confirm a clinical diagnosis of progressive disease by imaging.

All efforts will be made to ensure that the imaging equipment, contrast agent, and person (investigator or radiologist) performing the evaluation is kept constant throughout a patient's course on study.

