8.5.2. Efficacy Follow-Up

Patients who were not discontinued from study drugs due to disease progression and meet criteria otherwise (e.g., discontinued for AE and no new anticancer therapy) will be followed every 8 weeks (\pm 7 days) until disease progression, administrative issues, start of other anticancer therapy or any other reason listed in Section [8.4](#), whichever occurs first.

If the patient refuses to return for these visits or is unable to do so, every effort should be made to contact the patient or patient's guardian by telephone to determine the patient's disease status and survival.

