10. **For Dose Escalation and Dose Expansion Cohorts 1-5 Only:** ECGs will be performed in triplicate within a 5-minute window **prior** to Pamiparib PK assessments on Day -2 or Days 1 and 15. ECGs collected on the days of PK assessment will be performed on a machine provided by the sponsor and will be sent to a central reader. The same machine should be used for each patient whenever possible.
11. Hematology includes hemoglobin, platelet count, white blood cell count, neutrophil count, and lymphocyte count. Chemistry includes albumin, alkaline phosphatase, alanine aminotransferase, aspartate aminotransferase, blood urea nitrogen, chloride, creatinine, glucose, lactate dehydrogenase, phosphate, potassium, sodium, total bilirubin, and total protein.
Urinalysis includes blood, glucose, ketones, protein, red blood cells, and white blood cells.
In the event of clinically significant laboratory results, such as neutropenia (absolute neutrophil count $< 1000/\text{mm}^3$), thrombocytopenia (platelets $< 50,000/\text{mm}^3$), or Grade ≥ 3 clinical chemistry toxicity (per NCI CTCAE v4.03), these assessments will be conducted as frequently as the investigator feels is necessary until toxicity resolves to Grade ≤ 2 .
12. Screening blood and urine tests must be performed within 14 days of Day 1. If they were performed within 4 days of Day 1 they do not need to be repeated on Cycle 1 Day 1.
13. If urine protein is $\geq 2+$ by dipstick, a 24-hour urine for total protein and a random urine for total protein and creatinine will be obtained and evaluated (Section 7.6.3).
14. Only in women of childbearing potential; a serum pregnancy test must be taken ≤ 7 days from Cycle 1, Day 1.
15. For subsequent pregnancy testing on study and at EOT, urine pregnancy tests are allowed. If a urine pregnancy test is positive, a confirmatory serum pregnancy test is required.
16. A computed tomography (CT) or MRI scan of the thorax, abdomen, and pelvis plus other relevant evaluations as appropriate will be performed once every 8 weeks ± 7 days to assess all known disease. A CT/MRI taken within 28 days (Screening Period) of Cycle 1 Day 1 does not need to be re-taken. Patients without PD at the EOT Visit should be followed with tumor assessments every 12 weeks (± 7 days).

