10.2 CENSORING RULES

Table 3 shows the primary censoring rules for the derivation of PFS.

Table 3 Censoring Rules for Analysis of PFS

No.	Situation	Date of Progression or Censoring	Outcome
1	No baseline tumor assessments or no post baseline tumor assessment	Reference start date (e.g., C1D1)	Censored
2	Progression documented on scheduled visit or between scheduled visits	Date of first radiologic PD assessment	Progressed
3	No progression at the time of data cutoff or withdrawal from study	Date of last adequate radiologic assessment prior to or on date of data cutoff or withdrawal from study	Censored
4	Treatment discontinuation for undocumented progression	Date of last radiological assessment of measured lesions	Censored
5	New anticancer treatment started	Date of last radiological assessment of measured lesions prior to or on date of new anticancer treatment	Censored
6	Death before first PD assessment	Date of death	Progressed
7	Death between adequate assessment visits*	Date of death	Progressed
8	Death or PD after two or more consecutive missed visit**	Date of last adequate radiologic assessment before missed tumor assessments	Censored

9	A patient meets the criteria for more than 1 censoring rules above	Date of the earliest censoring date among all events	Censored
---	--	--	----------

Abbreviations: CR=complete response, PD=progressive disease, PR=partial response, SD=stable disease.

*Adequate tumor assessment is a radiologic assessment of CR, PR, SD, non-CR/non-PD or PD as determined by investigators or by IRC.

**More than one missed visit is defined if the duration between the last tumor assessment and death or PD is longer than 2 scheduled visits, which is 17 weeks (119 days).

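### Off-treatment tumour scans are set at 12 weeks in one schedule footnote and at 8 weeks elsewhere, and the SAP's 119-day missed-visit rule fits only the 8-week interval

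*Protocol*

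**What the plan says.** **Interval.** Footnote 16 of Protocol Appendix 1 Table 1 gives two intervals. Imaging "plus other relevant evaluations as appropriate will be performed once every 8 weeks" (± 7 days), and then "Patients without PD at the EOT Visit should be followed with tumor assessments every 12 weeks" (± 7 days). Section 7.7 says that patients who permanently stop study drugs before progression "will continue with regular tumor assessments as per protocol every 8 weeks" (± 7 days). Section 8.5.2 covers the same group ("e.g., discontinued for AE and no new anticancer therapy) will be followed every 8 weeks", ± 7 days). The Efficacy Follow-Up column of Table 1, which is marked for CT or MRI, is also headed 8 weeks with a 7-day window.

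**Censoring.** SAP Section 10.2, Table 3, row 8 censors a death or progression that follows two or more consecutive missed visits, at the last adequate scan before the gap. The table note defines that gap as "longer than 2 scheduled visits, which is 17 weeks (119 days"). SAP Section 6.3.2 applies the PFS censoring rules to DOR. There is no separate threshold for patients off treatment.

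**End of follow-up.** Section 8.5.2 ends off-treatment scanning at progression, "administrative issues, start of other anticancer therapy or any other reason listed in Section" 8.4, whichever is first; Section 7.7 is worded the same way. Section 8.4 lists reasons for stopping study drug, among them adverse events, investigator decision and noncompliance. The synopsis and Section 4.1 instead continue scans after a stop for reasons other than progression, and name their own end events.

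**The concern.** A site reading the schedule finds two scan intervals for the same patients in one table, and the footnote's interval also contradicts the body text. If some patients are scanned at 12 weeks and others at 8, progression off treatment is detected with different delays. The SAP's missed-visit rule would also act differently on the two groups: a threshold built for one interval misclassifies gaps under the other.

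The Section 8.4 reference raises a second question. It sends the reader to the list of reasons for stopping drug in order to decide when to stop scanning patients who have already stopped drug.

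**Working it through.** **Inputs.** Scan interval of 8 weeks (Sections 7.7 and 8.5.2, Efficacy Follow-Up column) or 12 weeks (footnote 16). Window of ± 7 days per scan in each case. Censoring threshold of 119 days (SAP Table 3 note).

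**Step 1: reproduce the SAP threshold.** Two intervals plus one 7-day window:
- 8 weeks: 2 × 56 + 7 = 119 days = 17 weeks. This matches the SAP exactly.
- 12 weeks: 2 × 84 + 7 = 175 days = 25 weeks. This does not match.

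Leaving out the window (112 days) or adding two windows (126 days) does not give 119 from 8-week spacing either. The rule is therefore built on 8 weeks plus one window.

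**Step 2: gap between the last scan and the next attended scheduled scan.** Nominal gap = (missed scans + 1) × interval. A window at each end moves it by up to 14 days.

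| Interval | Missed scans | Nominal gap (days) | Range with windows | Over 119 days? |
|---|---|---|---|---|
| 8 weeks | 0 | 56 | 42–70 | No |
| 8 weeks | 1 | 112 | 98–126 | Usually not |
| 8 weeks | 2 | 168 | 154–182 | Yes |
| 12 weeks | 0 | 84 | 70–98 | No |
| 12 weeks | 1 | 168 | 154–182 | Yes |

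One miss at 12 weeks produces the same gap as two misses at 8 weeks.

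**Step 3: detection delay.** If progression is equally likely at any time between scans and none is missed, the mean delay is half the interval: 56 / 2 = 28 days against 84 / 2 = 42 days. The difference is 14 days, or 14 / 30.4375 = 0.46 month. The longest delay is 56 against 84 days.

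**Step 4: illustration of how often the rule would act.** This rests on assumptions that are not in the documents: exponential time to progression after EOT with a median of 4 months, each scan missed independently, and progression found only at scheduled scans. Share of off-treatment progressions censored by the 119-day rule:

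| Scans missed | 8-week schedule | 12-week schedule |
|---|---|---|
| 5% | 1.3% | 7.9% |
| 10% | 3.5% | 15.5% |
| 20% | 10.1% | 29.8% |

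**Step 5: the end-of-follow-up wording.** Section 8.5.2 gives stopping for an adverse event as its example of a patient to be followed, then refers to Section 8.4, where adverse events are a listed reason. Taken literally, the end of the sentence can cancel its beginning. Section 4.1 gives a usable list instead: new anticancer therapy, progression, death, loss to follow-up, or withdrawal of consent for efficacy follow-up. The synopsis list is the same without new anticancer therapy.

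**The case against.** The best defence is that the intent is plain. Eight weeks appears in two body sections and in the schedule column, and the SAP agrees, so a careful site would scan at 8 weeks. That is likely, and nothing shows that sites have diverged. But footnote 16 is attached to the imaging row and names exactly this group of patients, so the conflict does not resolve itself.

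Three stronger readings are tempting, and the documents do not support them.

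- *A reader might infer that every progression after one missed 12-week scan is lost.* Section 7.7 allows a CT at any time if progression is suspected, and SAP Table 3 row 2 counts progression found between scheduled visits. If the day-84 scan is missed and an unscheduled scan shows progression on day 100, the event counts. So does a death between days 84 and 119. Nor is the 8-week schedule immune, since one miss can leave up to 126 days.
- *A reader might infer that scanning ends at once for patients who stop for toxicity, making the censoring informative.* Section 8.5.2 names those patients as ones to follow. Section 7.7, Section 4.1 and the synopsis continue scans after a stop without progression, and Section 8.4 itself allows a patient who withdraws from treatment to stay in follow-up. The reference is faulty, but it is not proof that scans stop.
- *A reader might infer that PFS and DOR as a whole are unreliable.* Only patients who stop all study drugs without progression and without new anticancer therapy are exposed. PFS and DOR are secondary, and no hypothesis is tested.

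**Conclusion.** The interval conflict stands as an internal contradiction in the current text, and the SAP threshold is consistent with only one side of it. Under footnote 16, progression first found at the scheduled scan after a single miss is censored, because the gap is 168 days (154 to 182) against a limit of 119. Under 8-week scans the corresponding gap is 112 days (98 to 126) and usually passes. Mean detection delay would be about 42 rather than 28 days, assuming progression is uniform between scans.

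The effect falls mainly on PFS and DOR. Any effect on the primary ORR is likely to be small. The effect on median PFS or DOR cannot be computed because the documents do not give the number of exposed patients, although in expansion cohorts of about 20–25 a few could matter. The Section 8.4 reference is a lesser fault: ambiguous wording to reconcile with Section 4.1 and the synopsis.

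**What to change.** 1. Change the off-treatment interval in footnote 16 to every 8 weeks (± 7 days). This agrees with Sections 7.7 and 8.5.2 and the schedule column, and leaves the SAP's 119 days valid. It requires no scans beyond those that Sections 7.7 and 8.5.2 already call for.
2. In Sections 7.7 and 8.5.2, replace the reference to Section 8.4 with the end events already listed in Section 4.1, and bring the synopsis into line on new anticancer therapy. SAP Table 3 row 5 already censors at that point. Pointing to Section 8.6 would not be enough. It covers leaving the study altogether and has no entry for a patient who declines further efficacy follow-up but remains in survival follow-up.

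If the sponsor did intend 12 weeks off treatment, Sections 7.7 and 8.5.2 and the schedule column must change instead. The SAP then needs an off-treatment threshold, which the same formula puts at 175 days.

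The cost is a wording amendment to the protocol; under the 8-week choice the SAP's 119-day rule does not change.
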